Anemic patients scheduled to undergo CABG, valve, or CABG/valve surgeries will be considered for the study. Patients who fulfill all the inclusion/exclusion criteria will be asked to participate in the study. The proportion of screen failures and eligible patients who refuse to participate will be recorded using a screen failure log. Patients who agree to be in the study and sign an informed consent form will be sequentially enrolled into the treatment group. The treatment group will receive up to three doses of EPO 300U/kg. The first dose of study medication will be administered up to 28 days before the day of surgery and the second will be administered 1-7 days before the day of surgery. These first two doses will be given at least 7 days apart. A third dose may be administered two to four days following surgery. All 3 doses will be administered subcutaneously and per surveillance strategy guidelines. In addition, supplementation

with IV iron (feraheme; 510mg delivered per IV infusion over a minimum of 15 minutes) will be given following the first two preoperative doses of EPO.

Differences in hemoglobin levels and reticulocyte counts from baseline to the day of surgery (preop to POD#0) and postoperative day five (POD#5), proportion of patients receiving erythrocyte transfusions and number of blood products (RBC, platelets and plasma) utilized and pre-defined clinical events (mortality, major cardiac, renal, neurological events [associated with anemia] and infection) will be assessed in all treated participants. Each patient will be enrolled in the study up to 28 days before the day of surgery and for up to 30 days following the day of surgery. This feasibility propensity-matched study will sequentially enroll 23 more treatment subjects to total 25. The propensity-matching control group will be comprised of 25 total “like” patients for comparison. The source of the data for the control group will be the Society of Thoracic Surgery (STS) Database, an institutional registry.

Study medications:

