- Patients in the treatment group will be seen again in a Patient Blood Management infusion room to receive a single subcutaneous injection of EPO 300U/kg and a 2nd IV iron infusion of 510mg, if iron reserves are believed to be inadequate (for a major hemorrhage) based on the result from the baseline iron panel and per Surveillance Strategy guidelines.

- Vitals signs, including heart rate, blood pressure, oxygen saturation, and temperature will be recorded before, during, and after drug administration.
- Patient will be monitored for any serious reactions (anaphylaxis, chest pain, dyspnea, seizures, severe headache, fever, nausea, vomiting, and diarrhea, an increase in blood pressure greater than 20mmHg above baseline systolic, systolic BP greater than 180mmHg and/or diastolic BP greater than 100mmHg, hypotension).
- Approximately 8mLs of blood will be drawn to obtain troponinT/CK-MB and reticulocyte count.
- The visit will last approximately 1 hour.

Day of Surgery

- We will monitor the patient's vitals (blood pressure, EKG, etc) as part of standard care.
- Approximately 8mLs of blood will be drawn to obtain hemoglobin concentration and reticulocyte count.

Post-Operative Dose

- Approximately 3mLs of blood will be drawn for a rotational thromboelastogram (RoTEM) measurement prior to redosing.
- Patients in the treatment group will receive a single subcutaneous injection of EPO 300U/kg two to four days following surgery, if they meet criteria as described in the surveillance plan.
- Vitals signs, including heart rate, blood pressure, oxygen saturation, and temperature will be recorded before and after injection.
- Patient will be monitored for any serious reactions (chest pain, dyspnea, seizures, severe headache, fever, nausea, vomiting, and diarrhea, an increase in blood pressure greater than 20mmHg above baseline systolic, systolic BP greater than 180mmHg and/or diastolic BP greater than 100mmHg).

Post-Operative Days #5, #7, #14

- On Day #5 approximately 8mLs of blood will be drawn to obtain a reticulocyte count, iron panel, AST/ALT.
- On Day #7 approximately 8mLs of blood will be drawn to obtain a reticulocyte count, CBC and creatinine (unless done as SOC).
- On Day #14 or at discharge approximately 6mLs of blood will be drawn to obtain a CBC and creatinine (unless done as SOC).

Clinical Outcomes

The primary objective is to assess the enrollment rate and adherence to the dosing protocol and

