surveillance strategies. We define successful adherence as adhering to dosing in $\geq 90\%$ of patients for $\geq 90\%$ of the doses deemed appropriate by the surveillance strategy. Secondary outcomes will include:

- 1) changes in hemoglobin levels and reticulocyte counts within the two groups from baseline to the day of surgery (preop to POD#0) and POD#5;
- 2) proportion of patients receiving erythrocyte transfusions and number of blood products (RBC, platelets and plasma) utilized;
- 3) incidence of pre-defined clinical events (mortality, major cardiac, renal, neurological events [associated with anemia] and infection) in each of the study groups.

[figure not shown]
These events will include myocardial infarction, prolonged low-output state, stroke, encephalopathy, duration of mechanical ventilation, renal insufficiency, and mortality and dialysis dependence at 30 days or discharge. Data from this feasibility study will be used for the power analysis and design of the larger RCT.

Clinical events will be defined using the following criteria: Society of Thoracic Surgery (STS)⁴² for stroke/transient ischemic attack (TIA), coma/encephalopathy, myocardial infarction (MI), prolonged ventilation, reoperation for bleeding or graft occlusion/revision, postoperative venous thrombosis, thromboembolic event, deep venous thrombosis and pulmonary embolism; RIFLE⁴³⁻⁴⁴ for acute renal injury (AKI), National Healthcare Safety Network (NHSN)⁴⁵ for surgical site infections (SSI); Surgenor SD et al.⁴⁶ for low output heart failure (LOHF); any life-threatening events (i.e., subject was at substantial risk of dying at the time of the adverse event) and in-hospital or 30-day mortality based on observation. Outcome data will be collected via contact with primary physician, public record review or by a follow-up telephone call by the research nurse.

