The cost of erythrocyte transfusions, EPO plus iron, direct hospital costs and direct margins associated with the care of those randomized in this pilot study will be recorded for future analysis of resource utilization. The duration of operating room time, intensive care unit and hospital length of stay will be collected. The total cost of erythrocyte transfusion will be based on four times the acquisition cost (\$1,200.00)⁴⁷ The cost of EPO and IV iron will be calculated based on recommended manufacturer suggested retail price at the time of publication and will include activity based costs of administering these treatments based on the protocol outlined in this study.

IV. STUDY PROCEDURES:

Time Line of Pilot Study

Note: Supplementation with intravenous iron (feraheme; 510mg delivered as an IV infusion) will only be administered following the first two preoperative doses of EPO (shown in diagram).

Consort Diagram of Pilot Study:

[figure not shown]

Table 1. SUBJECT SCHEDULE OF EVENTS

Test/evaluation & collected/required forms	7-28d PreOp	1-7d PreOp	POD0 PreOp	POD0 PostOp	POD 1	POD 2	POD 5	POD 7	POD 14
Inclusion & exclusion criteria	X								
Informed consent/HIPAA	X								
Demographics	X								
Medical History/Meds	X								
Physical examination	X	X	X	X	X	X	X	X	X
Body mass index	X								
Vital signs	X	X	X	X	X	X	X	X	X
ASA	X								
Laboratory									
CBC	S	S	S	S	S	S	S	S	S/X
Reticulocyte Count	S	X		X	S		X	X	
Iron panel**	S		X		S		X		
Creatinine	S	S	S	S	S	S	S	S	S/X
Troponin T/CK-MB		X		S	S	S/X			
AST/ALT		S			S		X		
Rotational Thromboelastogram (Rotem) ⁺				S		X			
12-lead EKG	S	S	S	S	S	S	S	S	
Record of Erythrocyte transfusion	X	X	X	X	X	X	X	X	X
Estimated blood loss				X	X	X			
Adverse Events	X	X	X	X	X	X	X	X	X
Patient Survey	X								
Protocol Compliance	X	X	X	X	X	X	X	X	X

S = Standard of Care laboratory tests routinely ordered per ICU care team

X = Not routinely ordered laboratory tests; obtained for research purpose only.

*Will obtain hemoglobin and creatinine on POD14 or before hospital discharge (whichever event occurs first)

**Iron panel includes ferritin, TIBC, iron, transferrin

⁺ Will obtain RoTEM EXTEM 2-4 days after surgery

Adverse events and survival will be reviewed at the time of hospital discharge and 30d following surgery.

V. SUBSTUDY PROCEDURES

Our study does not include any sub-studies.

VI. CRITERIA FOR INCLUSION OF SUBJECTS:

The inclusion criteria of subjects are as follows:

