The analysis of this feasibility study will be mainly descriptive and will focus on confidence interval estimation. Results from hypothesis testing will be treated as preliminary and interpreted with caution, as no formal power calculations have been carried out.

Analyses will be performed using parametric and nonparametric univariate and multivariate (where appropriate) statistical methods. Univariate distribution of all variables will initially be performed assessing their distribution with the use of scatter plots and histograms. These results will be used as guidelines in the application of both univariate and multivariate techniques. For descriptive purposes, continuous variables with normal distribution will be described using means, variance and standard deviations; otherwise, medians, interquartile and full ranges will be used. For variables showing distributions that are significantly away from normality, nonparametric statistical tests will be applied. Differences will be considered significant when $P < .05$.

Dichotomous variables will be presented as percentages and analyzed using chi-square or Fisher's exact tests as appropriate. Student t tests or Mann-Whitney U tests will be used to assess differences between independent continuous variables. The analysis of paired continuous variables (such as changes of hemoglobin level or reticulocyte counts from baseline to the day of surgery) will be performed with paired student t tests or Wilcoxon signed rank tests for normally or non-normally distributed variables, respectively. Multivariable regression techniques, including linear mixed models, will be used to analyze differences in continuous variables measured at several different points during the study between the groups (such as hemoglobin level, reticulocyte count, creatinine, etc.) accounting for the within-subject correlation of the data. All statistical analyses will be performed with SAS® software (Version # 9.3, SAS Institute Inc. Cary, NC).

References

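### Table 1 places the only day-of-surgery reticulocyte count after the operation, while the outcome it serves appears to be the response before surgery

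*Combined protocol and SAP*

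**What the plan says.** Secondary outcome 1 (section III, Clinical Outcomes) is "changes in hemoglobin levels and reticulocyte counts within the two groups from baseline to the day of surgery (preop to POD#0) and POD#5". Section XIII, Biostatistics, names "changes of hemoglobin level or reticulocyte counts from baseline to the day of surgery" as an example of a paired analysis, by t test or signed rank test.

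For the day of surgery, the visit text in section III states: "Approximately 8mLs of blood will be drawn to obtain hemoglobin concentration and reticulocyte count". It does not say whether the blood is drawn before or after the operation.

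Table 1 (section IV) does make the distinction. Its first four columns are "7-28d PreOp 1-7d PreOp POD0 PreOp POD0 PostOp". The reticulocyte row carries the marks "Reticulocyte Count S X X S X X", with blanks at POD0 PreOp, POD 2 and POD 14. The first X is therefore the 1-7 day visit and the second X is POD0 PostOp. By contrast, the CBC row is filled at every visit ("CBC S S S S S S S S S/X"), including both POD0 columns.

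**The concern.** Specific Aim 3 asks how far hemoglobin and reticulocytes rise after the EPO plus iron course. If the day-of-surgery reticulocyte count is drawn after the operation, it reflects the operation as well as the treatment. Section II, Background, reports that 79% of the site's anemic patients receive at least one erythrocyte transfusion. The transfusion strategy permits transfusion during bypass and intraoperatively, so donor cells can be present before a POD0 PostOp sample. No rule excludes or adjusts a value taken after transfusion.

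Two uses of the data would be affected. One is the paired change from baseline. The other is the pilot means and standard deviations, which Research Design and Methods says may be used to size the later randomized trial.

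**Working it through.** The plan gives no figure to reproduce here. The check sets Table 1 beside the text.

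**1. Table rows against the nine column headings** (– is blank; S is standard of care; X is research only).

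| Row | 7-28d PreOp | 1-7d PreOp | POD0 PreOp | POD0 PostOp | POD 1 | POD 2 | POD 5 | POD 7 | POD 14 |
|---|---|---|---|---|---|---|---|---|---|
| Reticulocytes | S | X | – | X | S | – | X | X | – |
| CBC | S | S | S | S | S | S | S | S | S/X |
| Iron panel | S | – | X | – | S | – | X | – | – |

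Each row has nine cells.

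**2. Reticulocyte research marks against the visit text.** The marks at 1-7 days, POD 5 and POD 7 agree with the draws listed for those visits. The POD0 mark agrees with the day but not with a time, since the text gives none.

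**3. What the outcome appears to require.**
- Aim 3 concerns the increase following treatment.
- Section II cites a hemoglobin rise of 1.4 to 2.1 g/dL on the day of surgery in earlier cardiac trials of EPO.
- Section XIII, Potential Benefits, describes gains in red cell mass and iron stores before surgery.
- POD#5 is listed separately as the postoperative point.

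Taken together these point to a sample before incision.

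**4. Whether another count could serve.** The last reticulocyte count before the operation is taken at the 1-7 day visit, which is also the second-dose visit. Doses 1 and 2 are at least 7 days apart, so this count can show a response to dose 1. It cannot show the response to dose 2 and is not a day-of-surgery value.

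**5. How the operation enters the measurement.**
- *Reticulocyte percentage:* bleeding removes young and mature cells in proportion, and plasma dilution leaves their ratio unchanged. Donor cells enlarge the denominator, so transfusion lowers the percentage.
- *Absolute count per volume:* hemodilution lowers it as well.

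The documents do not say which form is reported.

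**6. Direction, by illustration only.** Take native hemoglobin mass N = 11 g/dL × blood volume − 9 g/dL × blood loss. The ratio of the percentage after transfusion to that before is N / (N + units × g per unit). Only the 750 to 1,500 mL blood loss comes from the documents (section X). Assumed are a blood volume of 45 to 55 dL, hemoglobin of 11 g/dL before surgery and 9 g/dL in shed blood, 50 to 60 g hemoglobin per donor unit, no donor reticulocytes, and all units given before the sample.
- Low end: N = 11×45 − 9×15 = 360 g. One unit gives 360/(360+60) = 0.86; three units give 360/(360+180) = 0.67.
- High end: N = 11×55 − 9×7.5 = 537.5 g. One unit gives 537.5/(537.5+50) = 0.91; three units give 537.5/(537.5+150) = 0.78.

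This shows the direction. It is not an estimate of the bias in this study.

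**7. Between groups.** Aim 4 looks for a difference in transfusion. If treated patients receive fewer units, their percentages are lowered less than those of controls, and the contrast would be inflated in favor of treatment.

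**The case against.** The strongest reply is that the plan nowhere says the endpoint is preoperative. Aim 3 speaks only of an increase following the course, Aim 1 counts a postoperative dose as part of that course, and the bracketed definition of the outcome does not name a POD0 column. This stands as a limit: the preoperative reading is an inference from several places, not a quotation.

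A second reply is that the table may simply contain a slip. A mark in the wrong column still leaves nine cells, so the cell count proves little. The iron panel has a research mark at POD0 PreOp, yet the visit text lists no iron panel that day, and a swap of these two adjacent rows would explain both oddities. That is conjecture. If it is right, the table still needs correcting.

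Third, a reader might infer that the hemoglobin outcome is equally compromised and size the problem from the expected 750 to 1,500 mL of hemorrhage. The documents do not support this. A POD0 PreOp CBC is already scheduled, so the preoperative hemoglobin will exist; the plan only omits to say which POD0 value is analyzed. A fall in hemoglobin also says nothing about the size of any distortion in reticulocytes. Nor can one say without qualification that blood loss, dilution and transfusion all distort the count. For a percentage, only transfusion does so directly.

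Finally, the study is mainly descriptive, and its primary objective is enrollment and adherence. This limits the severity.

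**Conclusion.** The point holds in limited form. Under Table 1 as it stands, the only day-of-surgery reticulocyte count is postoperative, and the visit text does not correct this. The sample therefore does not match the quantity that the aims and background indicate is wanted.

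The conclusion rests on reading Table 1 as printed and on the inference that a pre-incision response is intended. The size of the distortion cannot be derived from the documents. The 79% figure is a past overall transfusion rate, not the share transfused before the POD0 PostOp sample.

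The between-group argument also needs control values at this time point. The POD0 count is research only and controls come from the STS registry, so such values are doubtful whichever column is used. The treated group's own change from baseline is affected regardless.

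Severity is minor: one time point of one secondary outcome in a feasibility study with 25 treated patients.

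**What to change.** - In Table 1, schedule the day-of-surgery reticulocyte count under POD0 PreOp. Either move the existing mark, or add one and label any POD0 PostOp count as descriptive only.
- Reconcile this with the day-of-surgery draw in section III, and check the iron panel mark in the adjacent row.
- State in Research Design and Methods, Day of Surgery, Clinical Outcomes and Biostatistics that the day-of-surgery value is the last sample before incision. For hemoglobin, name the POD0 PreOp CBC already scheduled.
- State whether reticulocytes are analyzed as a percentage or an absolute count.

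Moving the mark changes only a table and some wording, with the same number of draws. Keeping both counts needs a check against section X, which caps research blood at 8 mL per day: the existing draw of about 8 mL already uses that allowance.

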The decision to initiate and continue administering doses of EPO is based on evidence accrued from randomized controlled trials and clinical practice guidelines provided by multiple sub-specialty and international societies.^{14,40-41} Substantial heterogeneity exists in factors that could be included in a surveillance strategy to minimize the risk of a thrombotic event in this setting; with no one strategy proven to be superior. The surveillance strategy included in this protocol derives from, what we believe to be, the most current safety analyses of perioperative EPO use reflected in the literature. Implementing such surveillance methods are intended to minimize the possibly rare but potentially life-threatening adverse events. Risk factors considered in our surveillance strategy include: evidence of unstable angina or myocardial infarction, recent thrombotic event, hemoglobin levels associated with a higher risk of a

myocardial event, excessive thrombocytosis (platelet count $>300 \times 10^3/\mu\text{L}$) or laboratory evidence of a hypercoagulable postoperative state.

EPO dosing will be stratified based on patient risk (degree of perioperative anemia), type of procedure (CABG vs. valve) and laboratory data (Hb, RoTEM: MCF) in the following manner:

Initial dosing/Re-dosing of EPO plus IV iron (Prior to Surgical Procedure):

Therapy or a dose will **NOT** be administered in patients under the following conditions:

- Patients scheduled for a CABG procedure with Hb concentration $\geq 12.5\text{g/dL}$
- Patients scheduled for a cardiac valve procedure with Hb concentrations $\geq 13.5\text{g/dL}$
- Rate of rise in Hb level that exceeds 1g/dL in past 7 days (and not secondary to erythrocyte transfusion)^a
- Evidence of any new or evolving symptoms or signs suggesting the presence of myocardial ischemia, including chest pain, EKG changes, or elevation of laboratory cardiac biochemical (CK-MB, Troponin)
- Average of three diastolic blood pressures (over 1hr) $>100\text{mmHg}$ despite scheduled anti-hypertensive therapy.

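### The adherence success rule scores only EPO doses that the surveillance strategy allows, so a dose given despite a hold is never counted, although surveillance adherence is part of the primary objective.

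*Combined protocol and SAP*

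**What the plan says.** In the combined protocol and SAP, section III, Clinical Outcomes opens with "The primary objective is to assess the enrollment rate and adherence to the dosing protocol and" and then adds the surveillance strategies. The success criterion follows: "We define successful adherence as adhering to dosing in" at least 90% of patients, for at least 90% "of the doses deemed appropriate by the surveillance strategy". No other numeric adherence criterion appears.

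The surveillance strategy (section III, Surveillance Strategy for ESA Dosing) consists mainly of two lists of circumstances in which EPO is withheld.
- **Before surgery:** the list includes a hemoglobin limit by procedure, beginning "Patients scheduled for a CABG procedure with Hb concentration" at or above 12.5 g/dL. It also includes "Rate of rise in Hb level that exceeds 1g/dL in past 7 days", signs of myocardial ischemia, and a diastolic pressure limit.
- **After surgery:** the list covers hemoglobin, clot firmness on RoTEM, ischemia, and diastolic pressure.

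On exposure, section III states "The treatment group will receive up to three doses of EPO 300U/kg", and the study will "sequentially enroll 23 more treatment subjects to total 25". Specific Aim 2 names adherence to the surveillance strategy, and Table 1 has a protocol compliance row at every visit. Neither carries a threshold or a scoring rule. The Biostatistics section defines no adherence analysis.

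**The concern.** The objective has two parts and the success rule measures one of them. Following a surveillance strategy made of holds means, above all, not giving a dose when a hold applies. The rule's denominator leaves out exactly those decisions. A team that gave every scheduled dose without looking at the hold list would meet the rule, and the report could call that successful adherence.

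This matters because section X (Potential Risks) presents the surveillance strategy as an added protection against thrombotic events, and section III says the pilot is meant to inform the later trial about adherence to it. A success statement that cannot register failure to follow the holds would tell the designers of that trial nothing about whether the holds are workable.

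**Working it through.** **Inputs.** From section III: 25 treated patients, at most 3 EPO doses each (so at most 25 × 3 = 75 EPO decisions), and thresholds of 90% of patients and 90% of appropriate doses. The plan derives no figure for this rule, and the Biostatistics section reports no power calculation, so there is nothing to reproduce. The hold and violation counts below are assumptions for illustration.

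**Step 1: what the rule requires, read per patient.**
- Doses: with m appropriate doses, missing one leaves (m − 1)/m. For m = 3 this is 2/3 = 67%; for m = 2 it is 1/2 = 50%. Both are below 90%, so every appropriate dose must be given.
- Patients: 0.9 × 25 = 22.5, so at least 23 of 25 (92%); 22 of 25 is 88%. This 23 is unrelated to the 23 patients still to be enrolled.

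**Step 2: one patient.** Both pre-operative doses are appropriate and given, and a third is given despite a post-operative hold. The rule scores 2/2 = 100%. Of the three decisions, 2/3 = 67% followed the strategy.

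**Step 3: the whole group.** Suppose every appropriate dose is given, every patient has at least one, and h patients each receive at least one dose despite a hold. The rule scores 25/25 for any h. The share of patients with no such dose is (25 − h)/25:

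| h | Rule as written | Patients with no dose given despite a hold |
|---|---|---|
| 0 | 25/25 | 25/25 = 100% |
| 3 | 25/25 | 22/25 = 88% |
| 5 | 25/25 | 20/25 = 80% |
| 10 | 25/25 | 15/25 = 60% |

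**Step 4: an extreme case.** Assume 15 of the 75 decisions carry a hold and all 75 doses are given. The rule scores 25/25, with exact 95% lower limit 0.025^(1/25) = 0.863. All 15 holds were ignored. Each patient has at least one appropriate dose, hence at most 2 holds, so at least 15/2 = 7.5, rounded up to 8, patients are affected. At most 25 − 8 = 17 of 25 have no violation (68%; exact 95% CI 47% to 85%).

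**Step 5: patients with no appropriate dose.** Section VI admits hemoglobin below 13.0 g/dL. A CABG candidate at 12.5 to just under 13.0 g/dL is eligible but meets a pre-operative hold, and may also be held after surgery. The score is then 0/0, for which the rule gives no instruction.

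**Step 6: precision of a hold-violation rate.** If 0 of n holds are overridden, the exact 95% upper limit is 1 − 0.025^(1/n): 31% for n = 10, 22% for n = 15, 12% for n = 30.

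**The case against.** The best case for the plan has three parts.

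1. *Adhering to dosing can be taken to include withholding.* The stated denominator is appropriate doses, and a withheld or wrongly given dose has no place in it. The wording would have to change before this reading worked.
2. *The sentence may be a benchmark for the dosing half only, with surveillance adherence described under Aim 2 and the compliance row of Table 1.* This stands in part. A reader might infer that overridden holds would go unrecorded; the documents do not support that. What is missing is the label on the rule and a companion result.
3. *This is a pilot with a mainly descriptive analysis.* This stands, and it limits the harm. A reader might infer that a go/no-go decision is compromised, but the documents tie no such decision to the threshold.

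Three other readings go too far.
- One might say the unit is open and the 90% could be pooled over 75 doses. The sentence sets one percentage for patients and another for doses, and pooling discards the first.
- One might want a single 90% bar combining missed doses and overridden holds. Nothing in the documents calls for it.
- One might conclude from the sparse blood counts in Table 1 that the 7-day hemoglobin rise often cannot be checked. Blood counts are standard of care and available results are reviewed at baseline, so how often a usable pair exists is unknown.

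**Conclusion.** The point holds and is worth correcting. The success rule is blind to EPO given despite a hold, at any violation rate, so it cannot support a statement that the surveillance strategy was followed. This follows from the wording alone. The figures in steps 3 and 4 only illustrate it, and their counts of holds and violations are assumed. They should not be read as evidence that holds were or will be ignored. The consequence is confined to the pilot's claim about surveillance adherence; nothing here bears on whether the hold criteria themselves are well chosen.

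**What to change.** - **Keep the present rule and label it dosing adherence only.** State that it is read per patient: every appropriate EPO dose given in at least 23 of 25 patients.
- **Classify each scheduled EPO decision** as given with no hold, missed with no hold, withheld under a hold, given despite a hold, or hold not assessable.
- **Report the surveillance result beside the rule:** the given-despite-hold rate over decisions with a hold, with an exact 95% CI, and the number of patients with at least one such dose. Do not declare surveillance adherence successful from the dosing rule alone.
- **Report the number of decisions with an unassessable hold check,** and do not count these as respected holds.
- **Say how a patient with no appropriate dose is handled,** for example left out of the dosing rule's denominator and listed separately. The bar then scales: 0.9 × 23 = 20.7 gives 21 of 23; 0.9 × 20 gives 18 of 20.
- **Reconcile the blood-pressure hold before scoring.** Section X words it as a pressure above 180/100 mmHg. The surveillance lists use the average of three diastolic readings over an hour, above 100 mmHg despite scheduled treatment.

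The cost is a reworded endpoint and a few coded form fields. The dosing bar and the clinical rules are unchanged. The main limitation is the imprecision shown in step 6: the rate will describe this pilot but will not establish that violations are rare.
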